8.7.5. Secondary analyses

The secondary analyses will be conducted in the following study population/analysis set: pregnancies ending in singleton/multiple live birth. In these analyses any trimester pregabalin exposure will be considered versus each of the comparators as above. The monotherapy subset will be examined, sample size permitting.

Incidence rates (number of events/person-time contributed by live-born infants) of the postnatal neurodevelopmental outcomes will be reported according to any exposure to pregabalin and the predefined comparators. All incidence rates will be reported for any pregabalin therapy and the subset with pregabalin monotherapy.

For the postnatal neurodevelopmental outcomes, exposure will be defined at any time during pregnancy and the same comparators as above. Crude and PS-adjusted hazard ratios will be

estimated using Cox's proportional-hazards regression. In the event that too few postnatal outcomes are observed to estimate association, the number of cases and crude rates will be reported to the extent allowed by the data protection regulation.

8.7.6. Sensitivity analyses

To reduce the potential bias in the analysis of congenital malformations from not including pregnancies terminated due to known malformations, a sensitivity analysis including these will be conducted in the countries where this information is available (Denmark, Norway and Finland). The sensitivity analyses will be conducted in the following study population/analysis set: pregnancies ending in singleton/multiple live birth, stillbirth, or in therapeutic 2nd trimester induced abortion. The analyses in this population will assess the association of the first-trimester exposure to pregabalin and major congenital malformations, including all the comparators above. Separate descriptive tables will be produced and separate sets of PS will be estimated as appropriate for each contrast in the sensitivity analyses.

In another sensitivity analysis, crude estimates of association for the birth outcomes will be provided defining monotherapy of pregabalin, lamotrigine, and/or duloxetine by absence of other AED, selective serotonin reuptake inhibitors or benzodiazepines. By comparing magnitude and direction of change in the estimates of association obtained in this analysis and those in the main analyses of monotherapy, it will be possible to infer the direction and the amount of any potential unmeasured confounding, thus aiding interpretation of the results (triangulation⁵⁵).

All estimates of association will be reported with Wald 95% confidence intervals (CIs).

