8.3.3. Covariates and other population characteristic

Characteristics of the study population will include perinatal covariates and covariates of the mother. Perinatal covariates include calendar year of delivery, maternal age at conception, parity (number of live and still births prior to the on-study pregnancy); marital/cohabiting status; pregravid body mass index (BMI) as recorded at the first antenatal visit or via a hospital diagnosis of obesity; smoking during pregnancy as recorded at the first antenatal visit; single or multiple gestation; Caesarean delivery; and child's sex. Caesarean delivery and child's sex will be reported but will not be used for adjustment. Indication for pregabalin use in 12-months pre-LMP (epilepsy, neuropathic pain, GAD and related disorders) will be reported descriptively but will not be used for adjustment.

[figure not shown]
Covariates of the mother considered for adjustment (inclusion in propensity-score model) will include:

- calendar year of delivery;
- age in years at conception;
- marital/cohabiting status;
- smoking during pregnancy;
- Obesity (BMI ≥ 30 kg/m²) or a hospital diagnosis of obesity;
- Single or multiple gestation
- hospital-recorded morbidity based on inpatient and outpatient specialist care or proxy medication use in 12 months pre-LMP: migraine or other headache syndromes, other neurologic disorders, depression, bipolar disorder, alcohol abuse or dependence, drug abuse or dependence, hypertension, haematological diseases, diabetes, asthma, liver diseases, renal impairment, rheumatic diseases, obesity, disorders of female pelvic organs/genital tract, thyroid disorders, infections [infections will be assessed in 90 days pre-LMP]. In Finland, in addition to the hospital diagnoses, diagnoses from primary care are also available and will be used;
- indicators of maternal health care utilisation in the 12 months pre-LMP (number of inpatient and specialised outpatient encounters);
- for the outcome congenital malformations: maternal medication use each as a dichotomous variable, defined by at least one dispensing during the first trimester (AEDs, antidepressants, hypnotics, antipsychotics, analgesics, antihypertensives, non-steroidal anti-inflammatory drugs, drugs for peptic ulcer/gastroesophageal reflux, folic acid, drugs for in-vitro fertilization, thyroid hormones, systemic corticosteroids, and antiinfectives for systemic use);

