- for the outcomes other than congenital malformations: maternal medication use each as a dichotomous variable, defined by at least one dispensing during any trimester (AEDs, antidepressants, hypnotics, antipsychotics, analgesics, antihypertensives, non-steroidal anti-inflammatory drugs, drugs for peptic ulcer/gastroesophageal reflux, folic acid, drugs for in-vitro fertilization, thyroid hormones, systemic corticosteroids, and antiinfectives for systemic use).

[figure not shown]
Full list of the study variables and their operational definitions are provided in [Annex 3](#).

Figure 2. Examples of follow up period for neurodevelopmental outcomes during the study period

[figure not shown]
1.

2.

3.

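### The crude restricted-monotherapy analysis cannot show the amount of unmeasured confounding, as section 8.7.6 says it will

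*Protocol*

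**What the plan says.** The second sensitivity analysis in Protocol section 8.7.6 is crude by design: "In another sensitivity analysis, crude estimates of association for the birth outcomes will be provided". In it, a woman counts as on monotherapy only if she also had no SSRI and no benzodiazepine, on top of the usual requirement of no second AED. The section then sets these results against the main monotherapy results, looks at how far and which way they move, and concludes that "it will be possible to infer the direction and the amount of any potential unmeasured confounding". It presents this as an aid to interpretation, under the name of triangulation.

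Four other places bear on it:

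- Section 8.3.3 lists co-medication among the covariates for the PS model. For malformations each class is "defined by at least one dispensing during the first trimester (AEDs, antidepressants, hypnotics, antipsychotics, analgesics" and so on; for the other birth outcomes it is "defined by at least one dispensing during any trimester (AEDs, antidepressants, hypnotics, antipsychotics, analgesics" and so on. Depression and bipolar disorder, from hospital diagnoses or proxy medication, are also listed. Benzodiazepines and anxiolytics are not named as classes.
- Section 8.3.1 defines main-analysis monotherapy by absence of other AEDs only. The unexposed group has no AED and no duloxetine. SSRIs are allowed in both.
- Section 8.7.3 gives crude and adjusted estimates for the main analyses. Section 8.7.3.1 lists 16 PS sets, of which 8 are monotherapy contrasts. None uses the restricted definition.
- The sentence in section 8.7.6 about separate PS sets belongs to the preceding paragraph, on second-trimester abortions.

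**The concern.** The variables used for the restriction are measured: the restriction can only be built from dispensing records. Removing users of measured drugs and seeing the estimate move mainly shows what those drugs, and whatever goes with them, were doing to the crude estimate. It is not a measurement of confounding by factors that the registries lack.

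The text also leaves open whether the restricted crude estimate is compared with the crude or the adjusted main estimate. Neither comparison isolates unmeasured confounding.

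The point matters because unmeasured confounding is the central threat to this study. Indication was identifiable for only 21% of first-trimester exposed pregnancies in the Danish pilot data (section 6), is not used for adjustment (section 8.3.3), and residual confounding is acknowledged (section 8.9). A diagnostic read in the stated way could report unmeasured confounding where there is none, or give reassurance where there is some.

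**Working it through.** The protocol states no figure on this point, so there is none to reproduce. It also gives no co-medication prevalences or effects. Those below are assumptions, shown over a range.

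**Formula.** For a binary factor with prevalence p_e in the exposed and p_c in the comparator, with PR = R on the outcome and a true pregabalin PR of 1:

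crude PR = [1 + p_e(R − 1)] / [1 + p_c(R − 1)]

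**1. Unexposed comparator, both groups restricted, no unmeasured confounding.** The restricted PR is 1.00, so the fall equals the main crude PR.

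| Use, exposed / unexposed | R | Factor |
|---|---|---|
| 30% / 3% | 1.2 | 1.06 / 1.006 = 1.05 |
| 40% / 4% | 1.3 | 1.12 / 1.012 = 1.11 |
| 50% / 5% | 1.5 | 1.25 / 1.025 = 1.22 |

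**2. Unexposed group left unrestricted.** Sections 8.3.1 and 8.7.6 name only the three drugs in the restricted definition. On that reading the restricted PR is 1/1.006 = 0.99, 1/1.012 = 0.99 and 1/1.025 = 0.98. The restriction alone puts it below the null. The fall is then by factors of 1.06, 1.12 and 1.25.

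**3. Active comparator, both groups restricted.** With 30% vs 20% and R = 1.2, the factor is 1.06/1.04 = 1.02. With 50% vs 20% and R = 1.5, it is 1.25/1.10 = 1.14. With 50% vs 10% and R = 2, it is 1.50/1.10 = 1.36. Unmeasured confounding is zero in each.

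**4. Unmeasured confounder unrelated to co-medication.** Take prevalence 40% vs 10%, R = 2, and no effect of co-medication. The main crude PR is 1.4/1.1 = 1.27 and the restricted PR is also 1.27. The change is nil although the unmeasured bias is 27%.

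**5. Restricted crude against adjusted main.** Suppose adjustment works fully, so the adjusted main PR is 1.00. Let smoking be 30% vs 14% after restriction, with R = 1.3. The restricted crude PR is 1.09/1.042 = 1.05. The difference is measured confounding by smoking.

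**6. Noise.** Take the protocol's N = 1000 exposed and 3% malformations, and ignore comparator variance. Because the restricted group is a subset, the variance of the change in log PR is about (0.97/0.03)(1/n_r − 1/1000), where n_r is the number left.

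- n_r = 700: SE = √0.01386 = 0.118, so the 95% noise factor is exp(1.96 × 0.118) = 1.26.
- n_r = 500: SE = √0.03233 = 0.180, so the 95% noise factor is exp(1.96 × 0.180) = 1.42.

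This is favourable to the plan, since 1000 counts all first-trimester exposed pregnancies in four countries and not monotherapy alone. Even so, chance alone can match or exceed the shifts in step 1.

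**The case against.** The best defence is that SSRI and benzodiazepine use may be a proxy for anxiety and psychiatric severity that the PS does not hold. Indication is kept out of the adjustment, and section 8.9 says that GAD is poorly captured by diagnosis codes. A change on restriction can then hint at confounding outside the model. This stands, but it supports a qualitative reading and not an amount.

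A crude-only analysis is also defensible on feasibility. Table 4 expects about 200 first-trimester pregabalin pregnancies each in Denmark and Norway. Removing 30-50% leaves 100-140 before AED polytherapy is excluded, or about 3-4 malformation cases at 3%. This stands as a reason for reporting crude estimates. It does not support the inference drawn from them.

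Three stronger readings are tempting, and the protocol does not support them:

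- *A reader might infer that PS adjustment already removes the whole shift.* SSRIs fall under antidepressants, but benzodiazepines are only partly covered by the listed classes. Section 8.7.3.1 also lets sparse covariates be dropped if a model does not converge.
- *A reader might infer that being crude is the only fault.* An adjusted-to-adjusted comparison would remove the mixing with measured covariates, but would still not give the amount of unmeasured confounding.
- *A reader might infer that the report will discount an adjusted association on this basis.* Nothing in the protocol says so. The PS-adjusted monotherapy estimates are produced regardless. There are other checks too: comparison across comparators (section 8.1) and, if feasible, discordant pregnancies within women (section 8.7.3.1).

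**Conclusion.** The planned crude analysis may be reported, but the stated inference from it is wrong in both directions: the estimate can move with no unmeasured confounding and stay still with a substantial amount. This conclusion is logical and does not depend on the assumed inputs. The sizes do. The range of 1.05-1.22 needs the assumed prevalences and effects and an unexposed group restricted in the same way, which the protocol does not state. The alternatives are 1.06-1.25 without that restriction, and values down to 1.02 against active comparators. The damage is limited to the interpretation of one supplementary analysis; the main estimates are unaffected.

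**What to change.** In section 8.7.6:

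1. Delete the claim that the change gives the amount of unmeasured confounding. Describe it at most as a qualitative indication, and say that no change does not rule out unmeasured confounding.
2. Where numbers permit, re-estimate the PS in the restricted populations with the procedure of section 8.7.3.1 and report adjusted as well as crude estimates. Compare crude with crude and adjusted with adjusted, and state this.
3. State that the unexposed comparator is also restricted to pregnancies without SSRI or benzodiazepine dispensing in the same exposure window.

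A bias analysis such as E-values for the adjusted PRs is optional. It would not measure the confounding actually present.

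Items 1 and 3 cost a few sentences and a filter on existing data. Item 2 means up to 8 contrasts × 4 countries = 32 further PS models with existing code. Confidence intervals will be wider, and some models may not converge where exposed pregnancies are few. In those countries only the crude estimate would be reported, and the report should say so.

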8.7.7. Meta-analyses

After the separate analyses in each participating country as specified in the tables in [Annex 3](#), aggregated level data on crude and adjusted estimates of association will be transferred to Aarhus University Hospital, Denmark for meta-analyses. Because of the similarities between the healthcare systems in the Nordic countries and the use of a common study protocol with well-defined selection of exposures, outcomes and covariates, the MAH does not expect the associations between the exposures and outcomes to vary substantially between countries and therefore a fixed-effects meta-analysis will be applied.⁵⁶ Country-specific crude and adjusted estimates of association for each prespecified contrast will be combined in a meta-analysis.⁵⁷ For each outcome the MAH will use the inverse variance method in the fixed effects meta-analyses, which is weighting the country-specific estimates of association by the inverse of the within-country variances. Heterogeneity of the estimates will be verified and a random-effects meta-analysis will be considered as an alternative should the estimates be found to vary significantly between countries. Results of the meta-analyses will be presented using a standard forest plot, reporting the country-specific overall crude and adjusted point estimates, and the pooled overall point estimate, all with 95% CIs.

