8.5. Study size

Table 4 shows estimated number of total pregnancies ending in live or stillbirth and pregnancies with exposures and indications potentially relevant for analysis.

Table 4. Estimated numbers of pregnancies ending in live or still birth for potentially analysis-relevant categories

	Denmark (2005-2016)	Finland (2005-2014)	Norway* (2005-2016)	Sweden (2006-2013)
Pregnancies ending in live/still birth	730,000	580,000	650,000	800,000
Pregnancies with dispensation of				
Pregabalin, first trimester	200	700	200	400
Pregabalin, any time during pregnancy	350	900	350	800
Lamotrigine, first trimester	2000	900	2000	1300
Lamotrigine, any time during pregnancy	2700	1100	2700	1800
Duloxetine, first trimester	400	500	400	500
Duloxetine, any time during pregnancy	800	600	800	1000

*Pilot data not available; estimated based on pilot data from Denmark due to similar s population size.

The estimated numbers of pregnancies ending in live or still birth for potentially analysis-relevant categories for Norway were unavailable at the time of the protocol writing but are estimated in Table 4 by imputing data from Denmark, where the number of pregabalin users was the lowest, to provide the most conservative estimate. Based on this and on each country’s population size, conservatively estimated achievable size for this study will be more than 1000 pregnancies exposed to pregabalin during the first trimester.^{20,51} Table 5 shows the maximum upper limit of the 95% confidence interval of risk ratio that can be ruled out with 80% probability, for different scenarios with respect to the size of the exposed and comparator groups conservatively assuming N=1000 to be the size of pregabalin-exposed pregnancies. This analysis assumes that the true underlying risk ratio is 1.0 (no association between pregabalin exposure and an endpoint). For example, assuming the background prevalence of major congenital malformations to be 3%, underlying pregabalin-associated RR, and allocation ratio of comparator to pregabalin of 119:1 (corresponding to pregabalin exposure prevalence 0.8%), the analysis will rule out a RR with an upper confidence limit of 1.65845.

Table 5. Maximum upper limits of 95% confidence interval for risk or prevalence ratios depending on the prevalence of selected outcomes representative of prevalence of various study outcomes

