8.7. Data analysis

All steps of the country-specific data analyses will be conducted separately in each participating country according to the description below. Each country will generate a set of identical analytic tables, according to the table shells, provided in [Annex 3](#).

After conducting the country-specific data analyses, country-specific datasets containing crude and adjusted estimates of association will be transferred to Aarhus University Hospital, Denmark, for meta-analyses.

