8.7.3. Estimation of prevalence ratios and hazard ratios

Crude and adjusted prevalence ratios and 95% Wald confidence intervals (CIs) for each birth outcome and a given population/contrast will be estimated using log-binomial regression.

Crude and adjusted incidence rate ratios and 95% Wald CIs will be estimated Cox's proportional-hazards regression for each postnatal outcome.

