8.7.4.1. Descriptive analysis

- Pregabalin use in pregnancy will be described as the number and proportion of pregnancies exposed in the first trimester, and in any trimester. Number and proportion of pregnancies with pregabalin monotherapy will be reported. Cumulative dose during first trimester and any trimester will be described based on the amount of dispensings during a relevant period. Use of lamotrigine and duloxetine will be similarly described.

- Distributions of the characteristics of the study population will be tabulated according to pregabalin exposure categories: first trimester (exposed/unexposed); any trimester (exposed/unexposed) and separately for the monotherapy subgroup. Categorical variables will be summarized using frequencies and proportions; continuous variables using either mean and standard deviation (SD), or median and interquartile range (IQR) as appropriate.
- Distribution of maternal and offspring characteristics in the study population will be tabulated according to pregabalin and the active comparator categories, as above. All descriptive tables will be constructed including stillbirths.
- Crude prevalence of the major congenital malformations will be reported according to first-trimester exposure to pregabalin (overall and in the subcategory of monotherapy) and each comparator (overall for all comparators including not exposed and in the subcategory of monotherapy for lamotrigine and duloxetine). In addition overall prevalence of malformations in the whole general population will be presented. Crude prevalence of the other birth outcomes (stillbirth, low birth weight, small for gestational age (SGA), preterm birth, low Apgar score at 5 minutes and microcephaly) will be reported according to any trimester exposure to pregabalin and each comparator, in the same fashion.

Major congenital malformation outcomes

Major congenital malformations (any, each major malformation type sample size permitting), among pregnancies ending in a live or a stillbirth pregnancies exposed to pregabalin during the first trimester will be compared against each of the comparators estimating crude and adjusted prevalence ratios in log-binomial regression.

Birth outcomes other than major congenital malformations

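### Inverse-variance pooling of country prevalence ratios is biased upward for outcomes at or below about 1%, because countries with no exposed case cannot contribute and chance-high countries gain weight

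*Protocol*

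**What the plan says.** Each country fits its own model. Section 8.7.3 states that crude and adjusted prevalence ratios with "95% Wald confidence intervals (CIs) for each birth outcome and a given population/contrast will be estimated using log-binomial regression". Under section 8.7, "country-specific datasets containing crude and adjusted estimates of association will be transferred to Aarhus University Hospital" for pooling.

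Section 8.7.7 then fixes the pooling: "For each outcome the MAH will use the inverse variance method in the fixed effects meta-analyses", that is, "weighting the country-specific estimates of association by the inverse of the within-country variances". Random effects are an alternative if the estimates differ significantly between countries. Nothing is said about a country with no exposed case.

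Table 4 (section 8.5) gives the expected exposed numbers for Denmark, Finland, Norway and Sweden: "Pregabalin, first trimester 200 700 200 400" and "Pregabalin, any time during pregnancy 350 900 350 800". Table 5 lists outcomes at 0.2% (nervous-system malformations, mental retardation), 0.6% (stillbirth, autism spectrum disorders), 1% (cardiac malformations, ADHD), 3% (any major malformation) and 10% (preterm birth, SGA).

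Two provisions touch on sparse data. Section 8.7.4.1 analyses malformations overall and "each major malformation type sample size permitting", without a threshold. Section 8.7.5 falls back to case numbers and crude rates when postnatal events are too few.

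**The concern.** The standard error of a log prevalence ratio is driven by the exposed cases, and here these are few in every country. Two things follow.

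- With zero exposed cases there is no finite log ratio and no Wald variance. The country's follow-up, which is evidence for a low ratio, is lost.
- With a very large comparator the variance is about 1/(exposed cases). The weight therefore rises with the same chance fluctuation that raises the estimate.

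Both push the pooled ratio upward. The study is a regulatory commitment that follows a reported threefold increase in malformations which a second study did not confirm. An estimator that inflates ratios for rare outcomes when there is no effect could create a false signal. The limitations in section 8.9 do not mention it.

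**Working it through.** **Table 5 reproduced first.** With 1000 exposed, an allocation ratio of 119:1, a true ratio of 1 and 80% probability:

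U = exp[(1.960 + 0.842) × √{((1 − p)/(1000p)) × (1 + 1/119)}]

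At p = 3% this gives 1.65844; section 8.5 states 1.65845. The other rows give 7.30, 3.14, 2.42 and 1.31, against 7.2, 3.1, 2.4 and 1.3 in the table. Table 5 therefore rests on one two-group comparison, not on four pooled country estimates.

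**Sparsity by country** (first trimester, Table 4 numbers, order Denmark/Finland/Norway/Sweden). P(no exposed case) = (1 − p)^n.

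| Prevalence | Expected exposed cases | P(no exposed case) | At least one country without a case |
|---|---|---|---|
| 0.2% | 0.4/1.4/0.4/0.8 | 0.67/0.25/0.67/0.45 | 95% |
| 0.6% | 1.2/4.2/1.2/2.4 | 0.30/0.015/0.30/0.09 | 56% |
| 1% | 2/7/2/4 | 0.13/0.001/0.13/0.02 | 26% |

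**Direction of the bias.** Let aᵢ be the observed and Eᵢ the expected exposed cases in country i. With a very large comparator, wᵢ ≈ aᵢ and the pooled log ratio is about Σaᵢ·ln(aᵢ/Eᵢ)/Σaᵢ. By the log-sum inequality this is never below ln(Σaᵢ/ΣEᵢ). Two examples at 0.2%, each with 3 cases observed and 0.4 + 1.4 + 0.4 + 0.8 = 3 expected, so observed/expected = 1.00:

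- All 3 in Finland: pooled ratio 3/1.4 = 2.14.
- 2 in Finland and 1 in Sweden: exp{[2·ln(2/1.4) + ln(1/0.8)]/3} = exp(0.312) = 1.37.

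**Size.** Simulation with 200,000 to 400,000 studies per scenario and a true ratio of 1 in every country. Cases are binomial, with Table 4 exposed numbers and comparators of about 730,000, 580,000, 650,000 and 800,000. The within-country variance is 1/a − 1/n₁ + 1/b − 1/n₀, where a and b are the cases among n₁ exposed and n₀ comparator pregnancies. Countries without a finite estimate get no weight. False positive means that the lower 95% limit exceeds 1, as a share of all studies (nominal 2.5%).

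| Against the unexposed | Median PR, inverse variance | False positive | Median PR, Mantel-Haenszel | False positive |
|---|---|---|---|---|
| 0.2%, first trimester | 1.76 | 16.6% | 1.00 | 3.3% |
| 0.6%, first trimester | 1.20 | 9.3% | 1.00 | 3.7% |
| 1%, first trimester | 1.11 | 7.1% | 1.00 | 3.2% |
| 0.6%, any trimester (stillbirth) | 1.12 | 7.2% | 0.98 | 3.4% |
| 3%, first trimester | 1.03 | 4.8% | 1.00 | 2.9% |

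Repeat runs agree to within 0.2 percentage points. Across all scenarios against the unexposed, including 0.2% any trimester, Mantel-Haenszel medians lie between 0.98 and 1.03 and false positives between 2.6% and 3.7%.

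**Active comparators** (first trimester).

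- Lamotrigine ("Lamotrigine, first trimester 2000 900 2000 1300"): median 1.22 and 5.5% at 0.6%.
- Lamotrigine or duloxetine: median 1.22 and 6.4% at 0.6%.
- Duloxetine: mean PR 1.31, 1.20 and 1.12 at 0.2%, 0.6% and 1%, with false positives of at most 1.6%.

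**Patches that do not cure it** (0.2%, first trimester).

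- A 0.5 zero-cell correction: median 1.44, false positives 12.3%.
- DerSimonian-Laird random effects: mean 1.88, false positives 13.6%.

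Dropped countries are not the only cause. In studies at 0.6% where every country has a case, the inverse-variance mean is 1.27, against 1.15 for observed/expected on the same data.

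**The case against.** Several counter-arguments have weight.

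- **The worst figures may never be reported.** At 0.2% in the first trimester only 3 exposed cases are expected in all four countries, and section 8.7.4.1 makes specific malformation types conditional on sample size. This stands, although the condition has no threshold. It does not cover stillbirth, a primary outcome with no such condition.
- **The handling of zero-case countries is not written down.** A zero-cell rule could sit in a statistical analysis plan that is not shown. That is fair: the loss of these countries follows from the method and is not a sentence in the protocol. What the protocol does fix is inverse-variance weighting, and a 0.5 correction leaves most of the bias.
- **The motivating outcome is barely touched.** For any major malformation the median is 1.03. This stands.
- **False signals do not arise for every comparator.** Against duloxetine the comparator cells are sparse too, and the error rate falls below nominal. This stands.

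A reader might also infer that the Table 5 precision figures fail as a whole. They do not at Table 4 counts. The inverse-variance upper limit falls below the Table 5 value in 75% of studies at 0.2%, 92% at 0.6%, 94% at 1%, 97% at 3% and 93% at 10% (first trimester), and in at least 97% of studies in every row for any-trimester exposure. Only the 0.2% first-trimester row misses 80%. A wider shortfall would need total exposure to drop to the 1000 that Table 5 assumes as a conservative floor, whereas Table 4 sums to 200 + 700 + 200 + 400 = 1500.

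**Conclusion.** The concern holds for outcomes at or below about 1% in the contrasts with the unexposed, lamotrigine and the combined comparator. Against the unexposed, with no true effect, the planned pooling overstates the median PR by 11% to 76% in the first-trimester scenarios and by 12% for stillbirth. It produces false positives about three to seven times as often as the nominal 2.5%. Against duloxetine there is a milder upward bias and no excess of false signals. At 3% the effect is small, and at 10% it is negligible (median 1.01). A blanket statement that the meta-analysis is invalid, or that Table 5 is wrong, is not supported.

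The figures assume Table 4 exposure numbers, Table 5 prevalences that are equal across countries, and crude counts. The propensity-score analysis gives exposed pregnancies a weight of 1 (section 8.7.3.1), so trimming aside the exposed counts are as sparse and the same mechanism applies. The Cox outcomes were not simulated. Severity: should be fixed before the country results are pooled.

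**What to change.** In section 8.7.7, replace inverse-variance pooling with country-stratified Mantel-Haenszel, or an equivalent count-based or likelihood pooling that uses the propensity-score-weighted comparator prevalence. For the adjusted contrast with the unexposed, this amounts to total observed exposed cases divided by the sum over countries of (number exposed × weighted comparator prevalence).

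- Apply it to all birth outcomes, or to outcomes chosen in advance by **expected** exposed cases. Do not switch on observed counts. A rule that keeps inverse variance only where every country has at least 5 observed exposed cases selects chance-high studies: among null studies that meet it, the median PR is 1.07 with about 7% false positives at 3%, and 1.79 at 1%.
- Use an interval that allows for comparator variability when the comparator is small (duloxetine, lamotrigine). Keep an exact or mid-P Poisson interval for the contrast with the unexposed only.
- Report observed and expected exposed cases by country, and the number of countries behind each pooled estimate.

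The cost is a change of wording and a few more aggregate numbers per country. Where small cells cannot be released, each country can send a log-likelihood profile instead.
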